Title : Woebot for Substance Use Disorders Phase 2 RCT: Digitally Delivered Intervention for Reducing Problematic Substance Use (SU sIRB) Short name: Anchor Study

Approval Period: 03/17/2023 - 05/11/2023

treatment condition.

Data flow:

Participants provide data by completing surveys. The Stanford team is the recipient of this data. Emails are shared with the Woebot team for the interventions, payment, and cross-checking for intervention contamination (i.e. commercial Woebot app use, WSUDs program use but are supposed to be in Education only group). Intervention contamination information will be shared by Woebot to Stanford. Participants also provide data by interacting with the Woebot app. Woebot Labs will share user data with the Stanford team, who will link the data to survey responses. The Stanford team will analyze the data and then share analyzed data with the Woebot team.

Quality checks (IRB modification 8/26/2022):

Protection against bot responses:

A question to detect bot activity will be in the screening questionnaire. This question will be a hidden survey field (i.e. human respondents will not be able to see the question), but a bot can pick up this question and answer. If there is an answer, the study team will consider the survey response to be from a bot and thus ineligible for participation. Set up procedures for REDCap Cloud are attached in Protocol Information section 16.

Protection against international respondents:

the study team will implement a check on IP Address using <https://IPhub.info> to: 1) Prevent responses from international IP addresses, which indicate a respondent from outside the U.S. (exclusion criteria); and 2) Block respondents from using a virtual private network (VPN) to take the survey, as the use of a VPN allows for concealment of international IP addresses. This IP address check will apply to all who screen for eligibility. Attached in Protocol Information section 16 is an updated version of survey, with a new message to let respondents know about the IP address check. No changes are needed to the screening consent form, as it includes collection of IP address.

Rationale for the IP address check: This study is completely remote and will be using social media recruitment methods, where other studies have encountered survey responses from spammers and bots. Fraudulent survey responses to online surveys have been problematic, as highlighted in the manuscript found on DOI: 10.1017/psrm.2020.6

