a) State the following: (i) the number of participants expected to be enrolled at Stanford-affiliated site(s); (ii) the total number of participants expected to enroll at all sites; (iii) the type of participants (i.e. students, patients with certain cancer, patients with certain cardiac condition) and the reasons for using such participants.

N=400 (nationally) will be invited to participate in this study and entered into the study on a rolling basis. Inclusion criteria include: all genders aged 18-65 years, meet CAGEAID score of 2+ (WSUDs is designed for substance use); access to the apps on smartphone, be available and committed to engage with app and complete assessments, be willing to provide working email address (to distribute incentives), working

Title : Woebot for Substance Use Disorders Phase 2 RCT: Digitally Delivered Intervention for Reducing Problematic Substance Use (SU sIRB) Short name: Anchor Study

Approval Period: 03/17/2023 - 05/11/2023

telephone number (for interview portion and follow ups), and be literate in English (as educational materials and W-SUDs conversational and video materials will be in English). Exclusion criteria include: pregnancy (as W-SUDs will not be specifically developed to address the unique needs of this population), history of severe drug/alcohol use, opioid misuse without medication-assisted treatment, and suicide attempt or opioid overdose within the past year.

b) State the age range, gender, and ethnic background of the participant population being recruited.

Recruitment efforts will seek to enroll a demographically diverse sample age 18-65. Substance disorders are prevalent in individuals of all genders, therefore all genders will be recruited as participants in the proposed study.

c) State the number and rationale for involvement of potentially vulnerable subjects in the study (including children, pregnant women, economically and educationally disadvantaged, decisionally impaired, homeless people, employees and students). Specify the measures being taken to minimize the risks and the chance of harm to the potentially vulnerable subjects and the additional safeguards that have been included in the protocol to protect their rights and welfare.

These populations are not being targeted but are also not excluded from the study. Exception: Pregnant women and children will be screened out.

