Identify inclusion criteria.

Inclusion Criteria:

Eligible participants for this trial must:

1. Have a smartphone
2. Endorse a substance use concern
3. Be between 18 and 65 years of age
4. Be available and committed to engage with the Woebot app
5. Be literate in English.(This is required for inclusion because all materials will be in English).

Identify exclusion criteria.

Exclusion Criteria:

1. Pregnancy (as W-SUDs will not be specifically developed to address the unique needs of this population)
2. Suicide attempt within the past year (12 months)
3. Symptoms of severe drug/alcohol history: History of delirium tremens; Experiencing hypertension, drenching sweats, seizures or confusion after stopping alcohol or drugs; Liver trouble (cirrhosis or hepatitis); Convulsions or GI bleeding due to drug/alcohol use
4. Opioid overdose within the past year (12 months)
5. Opioid misuse without medication-assisted treatment
6. Not residing in the U.S.
7. Ever used Woebot

i) Describe your screening procedures, including how qualifying laboratory values will be obtained. If you are collecting personal health information prior to enrollment (e.g., telephone screening), please request a waiver of authorization for recruitment (in section 15).

Screening

IRB modification 3.3.23: There will be a brief internet delivered (via Qualtrics or REDCap Cloud) screener that will ascertain if individuals who express interest in participating in the study meet inclusion criteria. The screener-battery will include the CAGE Questions Adapted to Include Drug Use (CAGE-AID); The sum of these 4 items creates a score that is used to determine eligibility based on level of problematic use.

Title : Woebot for Substance Use Disorders Phase 2 RCT: Digitally Delivered Intervention for Reducing Problematic Substance Use (SU sIRB) Short name: Anchor Study

Approval Period: 03/17/2023 - 05/11/2023

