Woebot for Substance Use Disorders Phase 2 RCT: Digitally Delivered Intervention for
Reducing Problematic Substance Use

NCT ID: 04925570

March 17, 2023

Descriptive statistics (means, frequencies) will be run to describe the sample, and the balance achieved by the randomization, and to examine ratings of program feasibility and acceptability. Missing data on individual survey items is anticipated to be minimal. As needed, individual participants' average score values may be imputed when missing individual items on a scale (e.g., PHQ-8). For the outcomes of interest, the target estimand is the intent to treat on the study population with no loss to drop-out of the study (i.e., this estimand incorporates noncompliance with the randomization's assigned level of intervention). We will examine predictors of study retention. Generalized Linear Models (multivariable models) will test for group differences in changes in the primary outcome and secondary outcomes. The dependent variables will be baseline to EOT (and baseline to 1-month follow-up) change scores. The models are used to adjust for baseline group differences and will apply weights to adjust for correlates of study retention. Participant weights will be calculated as the inverse of predicted probability values from a logistic regression model predicting EOT (and 1-month follow-up) retention.

Between-subject differences in baseline variables may be substantial (e.g., baseline number of substance use occasions) so the models will use change from baseline to a given time point (e.g., number of substance use occasions at EOT minus the number of substance use occasions at baseline). This trial, while not an exact replication, extends previous work with a waitlist control where the primary outcome was the change in baseline to EOT in substance use occasions. Thus, we separately analyze changes (a) from baseline to EOT, and (b) from baseline to 1-month.

Correlations also will be examined between W-SUDs engagement metrics and change in primary and secondary outcomes in the treatment group. Additionally, a per-protocol analysis will be limited to treatment participants who use W-SUDs at least 4 of 8 weeks and control participants who view at least half of the online psychoeducational fact sheets.

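### The supplementary per-protocol rule admits controls on fact-sheet viewing alone, so a control flagged for W-SUDs or Woebot use would still be analysed as education only

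*SAP*

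**What the plan says.** The SAP has no numbered sections; the rule is in its third paragraph. It says that "a per-protocol analysis will be limited to treatment participants who use W-SUDs at least 4 of 8 weeks", and for the comparison arm it names "control participants who view at least half of the online psychoeducational fact sheets". It sets no condition on Woebot or W-SUDs use by controls.

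Protocol section 2(a), under data flow, says that emails go to the Woebot team for several purposes, one being "cross-checking for intervention contamination (i.e. commercial Woebot app use, WSUDs program use but are supposed to be in Education only group". It continues: "Intervention contamination information will be shared by Woebot to Stanford". The same section makes Stanford responsible for the analysis.

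Two other statements bear on the point. Protocol section 8(h) excludes anyone who meets the criterion "Ever used Woebot", which covers use before entry and not after randomisation. The SAP's first paragraph sets an intent-to-treat target and says that "this estimand incorporates noncompliance with the randomization's assigned level of intervention".

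**The concern.** A per-protocol contrast is meant to compare W-SUDs as received with education only as received. A control who opened half of the fact sheets and also used W-SUDs or the commercial app did not receive education only. The protocol's own term for that person is contaminated, yet the SAP rule lets the person stand as a compliant control.

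Two things are at stake. If Woebot use helps, keeping such controls pulls the per-protocol contrast toward no difference. And with no stated rule, the team must decide after seeing the data whether to drop flagged controls, which leaves a discretionary choice in an efficacy analysis.

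The documents make the situation plausible. Section 8(h) asks every participant to be willing to engage with the Woebot app, so controls are likely to know its name. Section 8(i) offers the general app without restriction to people who fail screening, so it can be obtained outside the trial.

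**Working it through.** The plan gives no contamination rate, effect size, SD, alpha or power, so there is no figure of its own to reproduce. The check is first a comparison of texts, then an illustration.

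**Comparison of texts**

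1. SAP, third paragraph: a control qualifies by fact-sheet viewing. No other condition is given.
2. Protocol section 2(a): commercial Woebot use, or W-SUDs use by a control, is defined as contamination, looked for by email, and reported to Stanford.
3. Remainder of the protocol and SAP: no sentence says how that information enters any analysis, and none removes a flagged control from the per-protocol set.
4. Result: a control who passes the viewing rule and is flagged by the cross-check is, as the rule reads, analysed as education only.

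**Size of the dilution**

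Let Δ be the true difference in mean change between W-SUDs and education only. Let c be the fraction of per-protocol controls who used W-SUDs or Woebot, and f the fraction of Δ that they gained. Assume that these controls would otherwise have changed like the rest.

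- Control mean change = (1 − c)μ + c(μ + fΔ) = μ + cfΔ
- Per-protocol contrast = Δ − cfΔ = Δ(1 − cf)
- Proportional loss = c × f

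| c (assumed) | f = 0 | f = 0.5 | f = 1 |
|---|---|---|---|
| 5% | 0% | 2.5% | 5% |
| 10% | 0% | 5% | 10% |
| 20% | 0% | 10% | 20% |

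**What the worst column would mean for power (illustration only)**

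Protocol section 8(a) states "N=400 (nationally) will be invited to participate in this study". Assume 1:1 allocation, so 200 per arm, two-sided alpha 0.05 and SD 1. Take Δ as the effect detectable with 80% power: √(2/200) × (1.960 + 0.842) = 0.280 SD. With f = 1 the contrast is 0.280 × (1 − c).

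| Per arm | c = 0 | c = 5% | c = 10% | c = 20% |
|---|---|---|---|---|
| 200 | 80.0% | 75.9% | 71.3% | 61.1% |
| 100 | 50.8% | 46.9% | 43.0% | 35.4% |

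With f = 0 dilution costs no power.

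**What exclusion would cost in numbers**

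Take 200 per arm with 20% of controls removed, leaving 160. The standard error is √(1/200 + 1/160) = 0.106, and 0.280/0.106 − 1.960 ≈ 0.68, which gives power of about 75%. That compares with 61.1% if flagged controls are kept and f = 1, and with 80.0% if they are kept and f = 0. This ignores any selection effect of the exclusion.

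**The case against.** The strongest reply is that little depends on this analysis. The target estimand is intent to treat and takes in noncompliance by design. The per-protocol analysis is one added sentence, with no hypothesis or power claim attached. Under the dilution model the error runs toward the null, so it would not manufacture support for W-SUDs. All of this stands, and it limits the importance of the point. A reader might infer that the primary result is compromised. It is not: a contaminated control belongs in the intent-to-treat analysis as randomised.

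A second reply is that the SAP sentence states a necessary condition and does not say that known crossovers stay in. That is fair as a reading: the plan is silent and does not record a decision to keep them. But the rule as written gives no ground for removing them, and the team would be acting outside it if they did.

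A third is that heavy W-SUDs use by a control is unlikely. Section 2(a) puts each group's instructions on a private email or study-only page and keeps participants unaware of the other group's content. This too stands. The commercial app is the likelier route, and section 8(i) describes it as a general version not aimed at substance use. So f could be close to 0, and a reader should not take 20% as the expected loss. Nor do the documents show that the more engaged controls are the ones who look for another app; the opposite is as easy to imagine.

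Finally, part of the protocol is redacted, and section 2(a) refers to an attached protocol that is not among the public documents. The finding is therefore limited to the available text, though the SAP sentence itself is intact.

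**Conclusion.** The point holds for the supplementary per-protocol analysis only. Its control-arm rule ignores contamination information that the protocol plans to collect, so an identified crossover would be analysed as education only. The intent-to-treat analysis is unaffected.

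The loss is c × f of the true effect: about 0% to 20% for c up to 20% and f from 0 to 1. Both are assumptions, and values near the bottom are realistic if contamination is mostly use of the general app. The direction, toward the null, rests on W-SUDs being beneficial and on flagged controls being otherwise like the others. If they differ in prognosis, the direction is not certain.

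A reader might also infer that commercial-app use should disqualify W-SUDs-arm participants at any time up to the 1-month assessment. The documents do not support that. Section 9(a) foresees discomfort when access to the intervention ends after 8 weeks. Someone who then turned to the commercial app would be dropped despite having complied throughout treatment, and this selection would differ between the arms.

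**What to change.** In the SAP's per-protocol sentence, define per-protocol controls as those who viewed half or more of the fact sheets and were not flagged by the section 2(a) cross-check for W-SUDs or commercial Woebot use during the 8-week intervention period. For the 1-month analysis, count control-arm flags up to that assessment. If the cross-check gives no dates, count any control-arm flag during the study.

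Do not exclude W-SUDs-arm participants for commercial-app use after week 8. Report the number flagged in each arm. Keep everyone as randomised in the intent-to-treat analysis.

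The change takes a few lines of SAP text and uses information already planned. Its costs are a slightly smaller per-protocol set and one more post-randomisation selection variable, in a set that is already selected that way. The flag is also imperfect. An email match will miss people who use a second address, a possibility that section 2(a) itself recognises when it deals with spamming. The protocol states no amount of use either, so brief use may be flagged along with sustained use. The counts by arm let a reader judge how much this matters.
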